10.3 Responsibilities of the investigator and IRB/IEC

Before initiating a trial, the investigator/institution must obtain approval/favorable opinion from the IRB/IEC for the trial protocol, written informed consent form, consent form updates, subject recruitment procedures (e.g., advertisements) and any other written information to be provided to patients/subjects. Prior to study start, the investigator is required to sign a protocol signature page confirming his/her agreement to conduct the study in accordance with these documents and all of the instructions and procedures found in this protocol and to give access to all relevant data and records to Novartis monitors, auditors, Novartis Quality Assurance representatives, designated agents of Novartis, IRBs/IECs, and regulatory authorities as required. If an inspection of the clinical site is requested by a regulatory authority, the investigator must inform Novartis immediately that this request has been made.

10.4 Publication of study protocol and results

The key design elements of this protocol will be posted in a publicly accessible database such as clinicaltrials.gov. In addition, upon study completion and finalization of the study report the results of this trial will be either submitted for publication and/or posted in a publicly accessible database of clinical trial results.

10.5 Quality Control and Quality Assurance

Novartis maintains a robust Quality Management (QM) system that includes all activities involved in quality assurance and quality control, including the assignment of roles and responsibilities, the reporting of results, and the documentation of actions and escalation of issues identified during the review of quality metrics, incidents, audits and inspections.

Audits of investigator sites, vendors, and Novartis systems are performed by Novartis Pharma Auditing and Compliance Quality Assurance (CQA), a group independent from those involved in conducting, monitoring or performing quality control of the clinical trial. The clinical audit process uses a knowledge/risk based approach.

Audits are conducted to assess GCP compliance with global and local regulatory requirements, protocols and internal SOPs, and are performed according to written Novartis processes.

11 Protocol adherence

This protocol defines the study objectives, the study procedures and the data to be collected on study participants. Additional assessments required to ensure safety of patients/subjects should be administered as deemed necessary on a case by case basis. Under no circumstances

Novartis	Confidential	Page 78
Amended Clinical Trial Protocol Version 03 c	lean	Protocol No. CAIN457F3301

is an investigator allowed to collect additional data or conduct any additional procedures for any research related purpose involving any investigational drugs under the protocol.

Investigators ascertain they will apply due diligence to avoid protocol deviations. If an investigator feels a protocol deviation would improve the conduct of the study this must be considered a protocol amendment, and unless such an amendment is agreed upon by Novartis and approved by the IRB/IEC and health authorities, where required, it cannot be implemented. All significant protocol deviations will be recorded and reported in the Clinical Study Report.

11.1 **Protocol amendments**

White blood cell count	< 0.8 × LLN		
Neutrophils	< 0.9 × LLN		

14 Appendix 2: Liver event and Laboratory trigger Definitions and Follow-up Requirements

	Definition/ threshold
LIVER LABORATORY TRIGGERS	• $3 \times ULN < ALT/AST \le 5 \times ULN$
	• 1.5 x ULN < TBL \leq 2 x ULN
LIVER EVENTS	• ALT or AST > 5 × ULN
	• ALP > 2 × ULN (in the absence of known bone pathology)
	• TBL > 2 × ULN (in the absence of known Gilbert syndrome)
	• ALT or AST > 3 × ULN and INR > 1.5
	 Potential Hy's Law cases (defined as ALT or AST > 3 × ULN and TBL > 2 × ULN [mainly conjugated fraction] without notable increase in ALP to > 2 × ULN)
	Any clinical event of jaundice (or equivalent term)
	• ALT or AST > 3 × ULN accompanied by (general) malaise, fatigue, abdominal pain, nausea, or vomiting, or rash with eosinophilia
	Any adverse event potentially indicative of a liver toxicity*
*These events cover the following: here	atic failure fibrosis and cirrhosis and other liver damage-related

Table 14-1Liver Event and Laboratory Trigger Definitions

*These events cover the following: hepatic failure, fibrosis and cirrhosis, and other liver damage-related conditions; the non-infectious hepatitis; the benign, malignant and unspecified liver neoplasms TBL: total bilirubin; ULN: upper limit of normal

Table 14-2 Follow Up Requirements for Liver Events and Laboratory Triggers

		,	
Criteria	Actions required	Follow-up monitoring	
Potential Hy's Law case ^a	 Discontinue the study treatment immediately Hospitalize, if clinically appropriate Establish causality Complete liver CRF 	ALT, AST, TBL, Alb, PT/INR, ALP and γGT until resolution ^c (frequency at investigator discretion)	
ALT or AST			
> 8 × ULN	Discontinue the study treatment immediately	ALT, AST, TBL, Alb, PT/INR, ALP and yGT until resolution ^c (frequency at	
	Hospitalize if clinically appropriate	investigator discretion)	
	 Establish causality 		
	Complete liver CRF		
> 3 × ULN and INR > 1.5	 Discontinue the study treatment immediately 	ALT, AST, TBL, Alb, PT/INR, ALP and γGT until resolution ^c (frequency at	
	Hospitalize, if clinically appropriate	investigator discretion)	
	Establish causality		
	Complete liver CRF		
> 5 to ≤ 8 × ULN	Repeat LFT within 48 hours	ALT, AST, TBL, Alb, PT/INR, ALP and	
•	If elevation persists, continue follow-up monitoring	γGT until resolution ^c (frequency at investigator discretion)	
	 If elevation persists for more than 2 weeks, discontinue the study drug 		
	Establish causality		
	Complete liver CRF		

Criteria	Actions required	Follow-up monitoring
> 3 × ULN accompanied by symptoms ^b	 Discontinue the study treatment immediately Hospitalize if clinically appropriate Establish causality Complete liver CRF 	ALT, AST, TBL, Alb, PT/INR, ALP and γGT until resolution ^c (frequency at investigator discretion)
> 3 to ≤ 5 × ULN (patient is asymptomatic)	 Repeat LFT within the next week If elevation is confirmed, initiate close observation of the patient 	Investigator discretion Monitor LFT within 1 to 4 weeks
ALP (isolated)		
> 2 × ULN (in the absence of known bone pathology)	 Repeat LFT within 48 hours If elevation persists, establish causality Complete liver CRF 	Investigator discretion Monitor LFT within 1 to 4 weeks or at next visit
TBL (isolated)		
> 2 × ULN (in the absence of known Gilbert syndrome)	 Repeat LFT within 48 hours If elevation persists, discontinue the study drug immediately Hospitalize if clinically appropriate Establish causality Complete liver CRF 	ALT, AST, TBL, Alb, PT/INR, ALP and γGT until resolution ^c (frequency at investigator discretion) Test for hemolysis (e.g., reticulocytes, haptoglobin, unconjugated [indirect] bilirubin)
> 1.5 to ≤ 2 × ULN (patient is asymptomatic)	 Repeat LFT within the next week If elevation is confirmed, initiate close observation of the patient 	Investigator discretion Monitor LFT within 1 to 4 weeks or at next visit
Jaundice	 Discontinue the study treatment immediately Hospitalize the patient Establish causality Complete liver CRF 	ALT, AST, TBL, Alb, PT/INR, ALP and γGT until resolution ^c (frequency at investigator discretion)
Any AE potentially indicative of a liver toxicity*	 Consider study treatment interruption or discontinuation Hospitalization if clinically appropriate Establish causality Complete liver CRF 	Investigator discretion

^cResolution is defined as an outcome of one of the following: (1) return to baseline values, (2) stable values at three subsequent monitoring visits at least 2 weeks apart, (3) remain at elevated level after a maximum of 6 months, (4) liver transplantation, and (5) death.

15 Appendix 3: The classification criteria for psoriatic arthritis (CASPAR)

To meet the Classification of Psoriatic Arthritis (CASPAR) criteria for diagnosis of psoriatic arthritis according to (Taylor et al 2006), a patient must have inflammatory articular disease (joint, spine or entheseal) and at least 3 points (out of 6) from the following 5 categories:

- 1. Evidence of current psoriasis, a personal history of psoriasis, or a family history of psoriasis:
 - Current psoriasis is defined as psoriatic skin or scalp disease present today as judged by a rheumatologist or dermatologist.* (2 points)
 - A personal history of psoriasis is defined as a history of psoriasis that may be obtained from a patient, family physician, dermatologist, rheumatologist, or other qualified health care provider. (1 points, only if current psoriasis is NOT present)
 - A family history of psoriasis is defined as a history of psoriasis in a first- or seconddegree relative according to patient report. (1 points, only if current psoriasis or personal history of psoriasis is NOT present)
- 2. Typical psoriatic nail dystrophy including onycholysis, pitting, and hyperkeratosis observed on current physical examination. (1 point)
- 3. A negative test result for the presence of rheumatoid factor by any method except latex. (1 point)
- 4. Either current dactylitis, defined as swelling of an entire digit, or a history of dactylitis recorded by a rheumatologist. (1 point)
- 5. Radiographic evidence of juxta-articular new bone formation appearing as ill-defined ossification near joint margins (but excluding osteophyte formation) on plain radiographs of the hand or foot. (1 point)

Total score:

(The CASPAR criteria eCRF will autopopulate the total number of points of the CASPAR criteria met by the patient. If the total score \geq 3, the patient meets CASPAR criteria for PsA diagnosis).

*Current psoriasis is assigned a score of 2; all other features are assigned a score of 1.

16 Appendix 4: ASAS Classification Criteria for Axial Spondyloarthritis (axSpA)

In patients with \geq 3 months back pain and age at onset < 45 years:

Sacroiliitis on imaging* plus ≥ 1 SpA feature	OR	HLA-B27 plus ≥ 2 other SpA features
*Sacroiliitis on imaging: Active (acute) inflammation on MRI highly suggestive of sacroiliitis associated with SpA Definite radiographic sacroilitis according to the modified NY criteria	SpA features: Inflammatory back pain Arthritis Enthesitis (heel) Uveitis Dactylitis Psoriasis Crohn's/colitis Good response to NSAIDs Family history for SpA HLA-B27 Elevated CRP	

17 Appendix 5: Modified New York criteria

Clinical criteria:

- Low back pain and stiffness for more than 3 months that improves with exercise, but is not relieved by rest.
- Limitation of motion of the lumbar spine in the sagittal and frontal planes.
- Limitation of chest expansion relative to normal values correlated for age and sex.

Radiological criterion:

• Sacroiliitis grade ≥ 2 bilaterally or grade 3–4 unilaterally.

Definite AS if the radiological criterion is associated with at least one clinical criterion.

-		

20 Appendix 8: Guidelines for administering the questionnaires for patient reported outcomes

Before trial start

Study coordinators should familiarize themselves with the PRO questionnaire(s) in the trial and identify any items where a patient's response might highlight issues of potential concern.

For example, one question in the SF-36 asks 'How much of the time in the past 4 weeks- have you felt downhearted and blue?' If a patient responds 'most or all of the time', then the study coordinator should inform the study investigator.

Before completion

- 1. Patients should be provided with the correct questionnaire at the appropriate visits and in the appropriate language.
- 2. Patients should have adequate space and time to complete the forms.
- 3. Questionnaire should be administered before the clinical examination.

During completion

- 1. Administrator may clarify the questions but should not influence the response.
- 2. Only one response for each question.
- 3. Also see "Addressing Problems and Concerns".

After completion

- 1. Check for completeness and not for content*.
- 2. Check for multiple responses that were made in error.

*However, any response which may directly impact or reflect the patient's medical condition (e.g. noting of depression) should be communicated by the study coordinator to the investigator).

Addressing problems and concerns

Occasionally a patient may have concerns or questions about the questionnaires administered. Guidance related to some of the most common concerns and questions are given below.

The patient does not want to complete the questionnaire(s)

Tell the patient that completion of the questionnaire(s) is voluntary. The goal is to better understand the physical, mental and social health problems of patients. Emphasize that such information is as important as any other medical information and that the questionnaire(s) is simple to complete. Suggest that the questionnaire(s) may be different from anything the respondent has filled in the past. If the patient still declines, retrieve the questionnaires. Record the reason for the decline and thank the patient.

The patient is too ill or weak to complete the questionnaire(s)

In these instances, the coordinator may obtain patient responses by reading out loud each question, followed by the corresponding response categories, and entering the patient's response. No help should be provided to the patient by any person other than the designated study coordinator. The coordinator should not influence patient responses. The study coordinator cannot translate the question into simpler language and has to be read verbatim.

The patient wants someone else to complete the questionnaire(s)

In no case should the coordinator or anyone other than the patient provide responses to the questions. Unless specified in the study protocol, proxy data are *not* an acceptable substitute for patient self-report. Patients should be discouraged from asking a family member or friend for help in completing a questionnaire.

The patient does not want to finish completing the questionnaire(s)

If non-completion is a result of the patient having trouble understanding particular items, ask the patient to explain the difficulty. Re-read the question for them *verbatim* but do not rephrase the question. If the respondent is still unable to complete the questionnaire, accept it as incomplete. Thank the patient.

The patient is concerned that someone will look at his/her responses

Emphasize that all responses are to be kept confidential. Point out that their names do not appear anywhere on the questionnaire, so that their results will be linked with an ID number and not their name. Tell the patient that his/her answers will be pooled with other patients' answers and that they will be analyzed as a group rather than as individuals. Tell the patient that completed forms are not routinely shared with treating staff and that their responses will only be seen by you (to check for completeness) and by the investigator. Any response which may directly impact on or reflect their medical condition (e.g. noting of severe depression) will be communicated by the coordinator to the physician.

The patient asks the meaning of a question/item

While completing the questionnaire, some patients might ask the meaning of specific items so that they can better understand and respond. If this happens, assist the patient by rereading the question for them *verbatim*. If the patient asks to interpret the meaning of an item, do not try to explain it, but suggest that he/she use his/her own interpretation of the question. Patients should answer the questions based on what *they* think the questions mean.

General information about all questionnaire(s):

All questionnaires have to be completed by the patients in their local languages using an electronic device. The questionnaires should be completed by the patients in a quiet area free from disturbance, and before any visit assessments. Patients should receive no help from family members; if questions cannot be answered alone (due to problems with reading or understanding), then the doctor or nurse should read the questions and record the patient's responses without influencing their answers. The information provided is strictly confidential and will be treated as such. If a patient has missed a question or given more than one response

per question, then this should be brought to patient. Incomplete questions should not be accepted without first encouraging the patient to complete unanswered questions.

The investigator must complete the patient/visit information on the electronic device and ensure that the center number, patient's number and initials are identical to the Case Record Form. As there are no source data for this questionnaire, the data queries will be restricted to patient/visit information.

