ICH	International Conference on Harmonization of Technical Requirements for
	Registration of Pharmaceuticals for Human Use
IEC	Independent Ethics Committee
IFU	Instructions for Use
IL	Interleukin
IRB	Institutional Review Board
IRT	Interactive Response Technology
IUD	Intrauterine Device
IUS	Intrauterine System
i.v.	intravenous(ly)
LEI	Leeds Enthesitis Index
LFT	Liver function test (raised serum transaminases and/or bilirubin levels)

MASES	Maastricht Ankylosing Spondylitis Enthesitis Score
MRI	Magnetic resonance imaging
MTX	Methotrexate
NRS	Numerical rating scale
NSAID	Non-steroidal anti-inflammatory drug
PCS	Physical Component Summary
PFS	Prefilled syringe
PRN	pro re nata
PRO	Patient Reported Outcome
PsA	Psoriatic arthritis
PsAMRIS	Psoriatic Arthritis Magnetic Resonance Imaging Score
RA	Rheumatoid arthritis
RF	Rheumatoid factor
SAE	Serious adverse event
S.C.	Subcutaneous(ly)
SF-36	Medical Outcome Short Form (36) Health Survey
SJC	Swollen Joint Count
SmPC	Summary of Product Characteristics
SpA	Spondyloarthritis
SUSAR	Suspected Unexpected Serious Adverse Reactions
TJC	Tender Joint Count
TNF/TNFα	Tumor necrosis factor
TNF IR / TNFα- IR	$TNF\alpha$ inhibitor inadequate responder
ULN	Upper limit of normal
VAS	Visual analog scale
WBC	White blood cell

Glossary of terms

Assessment	A procedure used to generate data required by the study.
Control drug	Any drug (an active drug or an inactive drug, such as a placebo) which is used as a comparator to the drug being tested in the trial.
DMARD	Disease modifying anti-rheumatic drug; in this study this term refers only to non-biologics.
Enrollment	Point/time of patient entry into the study at which informed consent must be obtained (i.e. prior to starting any of the procedures described in the protocol).
Inadequate response to TNF α	Active disease despite stable treatment with anti-tumor necrosis factor α (TNF α) for at least 3 months at a stable dose or for at least one dose in the case of lack of tolerance.
Study drug	The drug whose properties are being tested in the study; this definition is consistent with US Code of Federal Regulation 21 Section 312.3 and is synonymous with "investigational new drug" or "investigational medicinal product."
Study treatment	All study drug(s) whose properties are being tested in the study as well as their associated treatment controls.

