7.3 Liver safety monitoring

To ensure patient safety and enhance reliability in determining the hepatotoxic potential of an investigational drug, a standardized process for identification, monitoring and evaluation of liver events has to be followed.

The following two categories of abnormalities/adverse events have to be considered during the course of the study (irrespective of whether classified/reported as (S)AE):

- Liver laboratory triggers, which will require repeated assessments of the abnormal laboratory parameter
- Liver events, which will require close observation, follow-up monitoring and completion of the standard base liver CRF pages

Please refer to Table 14-1 in Appendix 2 for complete definitions of liver laboratory triggers and liver events.

Every liver laboratory trigger or liver event as defined in Table 14-1 of Appendix 2 should be followed up by the investigator or designated personal at the trial site as summarized below. Detailed information is outlined in Table 14-2 in Appendix 2.

For the liver laboratory trigger:

• Repeating the liver function test (LFT) within the next week to confirm elevation or resolution.

These LFT repeats must be performed using the central laboratory if possible. If this is not possible, then the repeats can be performed at a local laboratory to monitor the safety of the patient. Repeats laboratory must then be performed at central laboratory as soon as possible. If a liver event is subsequently reported, any local LFTs previously conducted that are associated with this event must be reported on the Liver CRF pages.

• If the elevation is confirmed, close observation of the patient will be initiated, including consideration of treatment interruption if deemed appropriate.

For the liver events:

- Repeating the LFT to confirm elevation as appropriate
- Discontinuation of the investigational drug if appropriate
- Hospitalization of the patient if appropriate
- A causality assessment of the liver event via exclusion of alternative causes (e.g., disease, co-medications)
- An investigation of the liver event which needs to be followed until resolution.

These investigations can include serology tests, imaging and pathology assessments, hepatologist's consultancy, based on investigator's discretion. All follow-up information, and the procedures performed must be recorded on appropriate CRF pages, including the liver event overview CRF pages.

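### Table 14-2 stops treatment at ALT/AST > 3 × ULN with INR > 1.5, but nothing requests PT/INR in asymptomatic patients at > 3 to ≤ 5 × ULN

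*Protocol*

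**What the plan says.** Table 14-1 separates laboratory triggers from liver events. ALT/AST above 3 and up to 5 × ULN is a trigger. "ALT or AST > 3 × ULN and INR > 1.5" is a liver event, with no upper limit on ALT/AST, so it also covers that band.

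For the INR criterion, the action in Table 14-2 is "Discontinue the study treatment immediately". Section 7.3 is softer for liver events in general, "Discontinuation of the investigational drug if appropriate", but it defers to the appendix: "Detailed information is outlined in Table 14-2 in Appendix 2". The mandatory stop therefore comes from Table 14-2.

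For a laboratory trigger, Section 7.3 asks for "Repeating the liver function test (LFT) within the next week to confirm elevation or resolution", followed by close observation if the elevation is confirmed. The Table 14-2 row "> 3 to ≤ 5 × ULN (patient is asymptomatic" asks for the same. Its follow-up column leaves monitoring to the investigator, with a further liver function test within 1 to 4 weeks. Other rows of the table list the follow-up tests by name, beginning "ALT, AST, TBL, Alb, PT/INR, ALP and".

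**The concern.** A mandatory stopping rule needs the value that decides it. Here the rule starts at 3 × ULN, but between 3 and 5 × ULN in a patient without symptoms no instruction leads to that value. A site could do everything the liver sections prescribe and continue dosing a patient who meets a criterion for immediate discontinuation, because INR was not measured.

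The stake is individual patient safety. The primary and secondary efficacy analyses are not affected.

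**Working it through.** No formula applies to the main point, so the check sets the relevant places side by side.

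**1. Scheduled tests.** Protocol Sections 6.5.5.1 and 6.5.5.2 list 5 hematology and 16 chemistry items, 5 + 16 = 21 in all. None is PT/INR. Section 6.5.5.3 is dipstick urinalysis, and Table 6-1 has no coagulation line.

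**2. The ALT/AST rows of Table 14-2.**

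| Row | Stop treatment | PT/INR named |
|---|---|---|
| > 8 × ULN | at once | yes |
| > 3 × ULN and INR > 1.5 | at once | yes, but INR is already known |
| > 5 to ≤ 8 × ULN | if it persists more than 2 weeks | yes |
| > 3 × ULN with symptoms | at once | yes |
| > 3 to ≤ 5 × ULN, asymptomatic | not stated | no |

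Four of the 5 rows name PT/INR. Leaving out the row where INR is already known, it is 3 of 4. Over the whole table, 7 of 11 rows name it: these four plus potential Hy's Law, isolated bilirubin > 2 × ULN, and jaundice.

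**3. Where the INR row makes a difference.** Patients above 8 × ULN, with symptoms, with a potential Hy's Law pattern or with jaundice already stop at once whatever the INR. The INR row therefore adds an immediate stop mainly for asymptomatic patients at > 3 to ≤ 8 × ULN. In the upper part of that range (> 5 to ≤ 8) PT/INR is among the follow-up tests. In the lower part (> 3 to ≤ 5) it is not.

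**4. Who is left.** A patient in the lower part who also has bilirubin > 2 × ULN, symptoms or jaundice moves to a row that lists PT/INR. The gap concerns asymptomatic patients with no other liver-event criterion.

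**5. Would the analysis show a missed case?** SAP Section 2.8.3 and its Table 2.8-3 have no INR item. Such a patient would be counted under ALT/AST > 3 × ULN, and nothing would show whether the INR criterion had been met.

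**6. Time to the next dose.** Table 6-1 schedules blood samples at Baseline (Day 1) and Week 2 (Day 15), with the next doses on Day 8 and Day 22. The gaps are 8 − 1 = 7 days and 22 − 15 = 7 days. From Week 4 dosing is every 4 weeks, so there is more room. The protocol does not say whether the week allowed for the repeat runs from the sample or from the result, so no exact margin can be given.

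**The case against.** **Graded escalation.** Both trigger rows, ALT/AST > 3 to ≤ 5 and bilirubin > 1.5 to ≤ 2 × ULN, get the same light first step, and 4 of the 11 rows omit PT/INR. The omission may be deliberate tiering. It is a fair description of the table, but it does not settle the matter: the INR stop is itself set at > 3 × ULN. Had it been meant only above 5 × ULN, the threshold would say so.

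**Meaning of LFT.** A reader might infer from the abbreviation list, "Liver function test (raised serum transaminases and/or bilirubin levels", that a repeat LFT excludes INR by definition. The documents do not support that. Exclusion criterion 17 counts alkaline phosphatase among the liver function tests, and the isolated ALP row asks for a repeat LFT that must include ALP, so the entry is not a closed panel. What stands is narrower: no text says that LFT includes PT/INR.

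**Safeguards.** These are substantial:
- Appendix 1 makes ALT/AST > 3 × ULN a notable value, sends it to the sponsor or CRO, and says that action on it should be discussed with them.
- Section 5.6.2 requires a stop for laboratory abnormalities that the investigator judges clinically significant and a safety risk.
- Section 7.3 allows interruption to be considered.
- Section 6.5.5 requires follow-up of clinically significant values.
- Section 11 allows further safety tests case by case.
- Exclusion criterion 17 bars entry above 2 × ULN.

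They lower the risk and may well prompt the test. None of them asks for INR.

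**Laboratory manual.** Section 6.5.5 leaves central laboratory details to a manual that is not among the documents. If it provides reflex PT/INR, the gap is one of cross-reference only. This objection stands.

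**Conclusion.** The point holds and is minor. For asymptomatic patients at > 3 to ≤ 5 × ULN with no other liver-event criterion, a mandatory stop depends on a discretionary test.

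A reader might go further and infer that the INR rule cannot operate in this band, or that such patients would be dosed on unnoticed. Neither follows. The investigator may order the test, the sponsor or CRO is told of the value, and action on it should be discussed with them.

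The number of patients is probably small. The documents give no incidence of such elevations, so no probability is offered.

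The conclusion assumes that the laboratory manual has no reflex PT/INR at > 3 × ULN. Footnotes a and b of Table 14-2 are missing from the available text, but their marks are on the Hy's Law and symptom rows, not on this one.

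**What to change.** Add PT/INR to the repeat sample already required within the next week, both in the trigger action of Section 7.3 and in the asymptomatic > 3 to ≤ 5 × ULN row of Table 14-2. If the laboratory manual already provides reflex PT/INR at > 3 × ULN, a cross-reference in those two places is enough.

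Where feasible, the result should be known before the next dose. This needs most care after the Baseline and Week 2 samples.

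The cost is a phrase in two places and one more assay, at a draw already planned, in a few patients. The downside is that INR > 1.5 in a patient on anticoagulants needs medical interpretation. Neither the exclusion criteria nor Table 5-1 bars anticoagulants, and the INR criterion has no exception for them. The medical team should decide how to read it; that is a side clarification and not a condition for the fix.
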